5.2. Sample Size and Power Calculations

Based on previous studies in the literature,^{4,43,44} this study is designed to detect a 4-point difference in the mean QuIC part A comprehension scores between the two study arms. This difference represents a 0.5 standard deviation difference and has been considered to represent a clinically meaningful difference in comprehension scores in previous studies. The sample size for a two-sample t-test will require 64 participants per group to detect a 4-unit difference between group means ($\alpha=5\%$, power=80%, standard deviation=8). Asymptotic relative efficiency of the Mann-Whitney test to the 2-sample t-test is 0.864 under any symmetric

distribution, which means that 15% more subjects will need to be recruited, leading to 74 per group or 148 in total. Another 25% is added to account for possible dropouts (e.g., patients consent for this study, but are subsequently not able to participate in the consent process for the BMT CTN parent clinical trial [e.g., due to disease progression or determined ineligible to participate]). The study will need to enroll 198 subjects (approximately 99 in each arm). The stratified randomization will eliminate possible association between trial and center strata and consent group assignment, which potentially increases power properties.

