5.5. Analysis Plan

The primary analysis will be performed using the intention-to-treat principle so that all randomized patients will be included in the analysis. The t-test or the Mann-Whitney test will be used if the t-test assumptions are violated. Secondary endpoints of subjective comprehension, anxiety, satisfaction, and information location will be analyzed with the Mann-Whitney test. The binary outcome of consent rates will be compared using the Fisher exact test. The above unadjusted analyses will be complemented by analyses that adjust for potentially confounding

variables in regression analyses. Generalized estimating equations (GEE)⁵⁰ will be used to control for effect of confounding variables (e.g., patient demographics, health literacy level, strata) and a potential consenter effect (as more than one clinician could be involved in the consent process at a clinical trial site). GEE with identity link will be used for comprehension, anxiety and satisfaction analyses. Information location will be analyzed with LOG link and LOGIT link with accrual outcome. Variance will be estimated with the sandwich estimator if the number of consenters is > 30; otherwise the “leave-one-consenter-out” jackknife variance estimation will be used.⁵¹ Exact logistic regression will be used with accrual if the problem of small counts appears. Otherwise Wald tests will be used for significance testing. All two-way interactions between the group indicator (ETRIC vs. standard) and confounding variables will be tested and added to the model if significant. It is expected that all confounders will be analyzed as fixed effects except for the consenter which will be the repeated factor in the GEE. The form of continuous predictors will be either linear, quadratic, or categorized depending on the number of clusters observed in the dataset. Every category in categorical variables will have at least 10 subjects otherwise we will consider merging with neighboring categories. The presence of missing data in excess of 10% will be addressed by developing an imputation model for missing components given the observed part. Then, the multiple imputations approach will be used to estimate regression parameters and their standard errors.⁵²

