BMT CTN #1205 Statistical Analysis Plan (SAP)

Drafted by: [name] on 9/17/16

PROTOCOL: Easy-to-Read Informed Consent (ETRIC) for Hematopoietic Cell Transplantation Clinical Trials

Protocol Synopsis:

The BMT CTN protocol #1205 titled “Easy-to-Read Informed Consent (ETRIC) for Hematopoietic Cell Transplantation Clinical Trials” is a randomized, multicenter, prospective comparative study of ETRIC or standard consent form to improve patient comprehension of BMT CTN parent clinical trials. The primary objective is to compare objective comprehension scores on the Quality of Informed Consent (part A) instrument between patients randomized to the ETRIC versus the standard consent arms. Secondary objectives are to compare the following measures between the two arms: (1) subjective comprehension scores on the Quality of Informed Consent (part B) instrument and the modified Deaconess Informed Consent Comprehension Test instrument, (2) state anxiety scores on State Trait Anxiety Inventory instrument, (3) satisfaction score, (4) time taken for information location, and (5) patient consent rates on parent clinical trials. Per the original study design, the target sample size was 160 patients with 80 on each arm ensuring 64 patients per arm to complete Quality of Informed Consent part A comprehension survey. An interim analysis revealed that the survey completion rate was lower than expected, and then the target sample size was increased to 198 with expected 99 patients per group and 64 per arm to complete the Quality of Informed Consent part A questionnaire.

Study Status and Publication Plan:

The study opened enrollment in November 2013 and closed in August 2016 when the targeted sample of 198 patients was enrolled. Two manuscripts are anticipated from this trial. The first manuscript will describe the qualitative study and will detail the barriers and facilitators that were identified on semi-structured interviews of participating site research and IRB personnel. The analysis for this manuscript has been completed. The second manuscript will present the analysis of the randomized study that is detailed in this statistical analysis plan. We plan to circulate the first draft of the manuscript to the protocol team for review within 6 weeks after the analysis has been reviewed.

Survey instrument scoring:

- The Quality of Informed Consent Parts A and B will be scored as described in (Joffe et al, 2001)

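### Protocol 5.2 bases 198 on 74 evaluable patients per arm, but the SAP expects only 64 to about 66 QuIC Part A completers per arm from the same 198, so the Mann-Whitney margin is not reached

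*SAP*

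**What the plan says.** **Protocol 5.2** sets a 4-point difference in mean QuIC Part A, SD 8, alpha 5% and power 80%, and obtains 64 per arm for a two-sample t-test. It then allows for the rank test: "Asymptotic relative efficiency of the Mann-Whitney test to the 2-sample t-test is 0.864", so that "15% more subjects will need to be recruited, leading to 74 per group or 148 in total". Finally, "Another 25% is added to account for possible dropouts", which leads to 198, about 99 per arm. The example given for these dropouts is that "patients consent for this study, but are subsequently not able to participate in the consent process for the BMT CTN parent clinical trial". No questionnaire completion rate is stated.

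**Protocol 5.5** fixes the order of the tests: "The t-test or the Mann-Whitney test will be used if the t-test assumptions are violated". The SAP (Primary Endpoint and Data Analysis) keeps that order, with a two-sided 5% level, and limits the primary analysis to patients who completed QuIC Part A. Its Patients to Include paragraph repeats the limit.

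**The SAP synopsis** reports that completion was lower than expected and that "the target sample size was increased to 198 with expected 99 patients per group and 64 per arm to complete" the questionnaire. Its missing-data paragraph expects about two thirds of participants to complete it. The SAP mentions neither the 74 per arm nor the Mann-Whitney inflation.

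**The concern.** One enrolment total carries two different evaluable numbers. Because the SAP's primary analysis uses completers, its completers are the patients that the protocol's evaluable number ought to describe. The protocol implies 74 per arm; the SAP expects 64 to about 66.

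The difference matters because the step from 64 to 74 was put there to protect the Mann-Whitney test. Someone reading only Protocol 5.2 would conclude that 198 patients give 80% power whichever primary test is used. At the completion the SAP expects, that margin has been used up by missing questionnaires, and neither document says so. If the fallback were used and the result were null, the stated basis for the sample size would mislead.

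**Working it through.** **Inputs.** Difference 4, SD 8, so d = 0.5; power 80%; base 64 per arm; efficiency 0.864; 25% dropout; 99 per arm (Protocol 5.2). Two-sided 5%, completers only, t-test first (SAP, Primary Endpoint and Data Analysis). 64 completers of 99 (SAP synopsis). About two thirds completing (SAP, Missing data).

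**1. Reproducing the protocol's 198.**
- t-test, noncentral t: n = 63.77, so 64 per arm.
- Mann-Whitney: 64 / 0.864 = 74.07 (or 64 × 1.15 = 73.6), so 74 per arm, 148 in total.
- Dropout: 148 / (1 − 0.25) = 197.3, so 198. The additive reading, 148 × 1.25 = 185, does not give 198, so the 25% is a loss fraction.

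The protocol's chain is sound and implies 74 / 99 = 74.7% evaluable.

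**2. What the SAP implies for the same 99 per arm.**
- 64 / 99 = 64.6% completing, 35.4% lost.
- 2/3 × 99 = 66 completing, 33.3% lost.
- Shortfall against 74: 74 − 64 = 10, or 74 − 66 = 8 per arm.

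**3. Power at each evaluable number.** Two-sample t power with d = 0.5. For Mann-Whitney, n is multiplied by the efficiency: 64 × 0.864 = 55.3, 66 × 0.864 = 57.0, 74 × 0.864 = 63.9. The near-normal efficiency 0.955 (3/π) is an assumption that the documents do not make.

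| Evaluable per arm | t-test | Mann-Whitney, 0.864 | Mann-Whitney, 0.955 (assumed) |
|---|---|---|---|
| 64 | 80.1% | 74.1% | 78.3% |
| 66 | 81.4% | 75.4% | 79.5% |
| 74 | 85.6% | 80.1% | 83.9% |

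**4. The same result as a detectable difference at 80% power.** For the t-test, 3.99 points at 64 per arm and 3.93 at 66. For Mann-Whitney at 0.864, 4.30 and 4.23 points, against 3.99 at 74 per arm.

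**The case against.** The strongest reply is that nothing the trial promises has failed. The t-test is the first choice, 64 per arm gives it 80.1%, and the protocol synopsis claims only 80% power for 0.5 SD. That is correct and limits the severity. A reader might infer that the trial is underpowered, or that it should have enrolled enough to keep 74 evaluable per arm: 74 / (2/3) = 111 per arm (222), or 74 / (64/99) = 114.5, so 115 per arm (230). The documents do not support that inference, because the t-test requirement is met at the expected completion.

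Second, the SAP sentence can be read as a brief history in which 64 is the required minimum, not a forecast. That is arguable for the sentence alone. But the missing-data paragraph separately expects about two thirds to complete, which is also below 74.7%.

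Third, the dropout example in 5.2 is only an example, so the 25% may have been meant to include unreturned questionnaires. That stands: the text does not prove that the two documents count different kinds of loss. It does not remove the discrepancy, since a total loss of 25% still disagrees with 33% to 35%.

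Fourth, a six-point loss for Mann-Whitney is not a firm figure. The value 0.864 is conservative, and the documents specify neither the score distribution nor what counts as violated assumptions. Simulation with assumed continuous shapes puts Mann-Whitney power at 64 per arm anywhere from about 75% (a light-tailed symmetric shape) to about 91% (a heavy-tailed one). Those shapes ignore the ties and ceiling of a bounded 16-item score, so they show only that the answer depends on the distribution. A reader should infer neither that the fallback certainly falls short nor that skewness would certainly rescue it.

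Fifth, the SAP also gives an earlier target: "Per the original study design, the target sample size was 160 patients with 80 on each arm". That is superseded and is not evidence of an error; the discrepancy lies wholly in current text.

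Protocol 5.5 also calls for an intention-to-treat primary analysis of all randomized patients, whereas the SAP uses completers. That is a separate inconsistency and this point does not settle it.

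**Conclusion.** The point holds and is minor. The protocol's arithmetic is right on its own terms, but the 74 evaluable per arm in 5.2 is not reached at the QuIC Part A completion the SAP expects. The gap is 8 to 10 patients per arm, and with it goes the margin meant for Mann-Whitney.

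For the first-choice t-test, 80% is still met, with almost no reserve at 64 per arm. For the fallback, power at the protocol's own efficiency is about 5 to 6 points below 80% (80 − 75.4 = 4.6; 80 − 74.1 = 5.9). Under near-normal efficiency the gap is about 2 points or less (80 − 78.3 = 1.7; 80 − 79.5 = 0.5).

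These figures assume a true 4-point difference, SD 8, equal arms, and completion as the SAP expects. The 64 is printed in the SAP; the 66 is two thirds of 99. The Mann-Whitney figures also use asymptotic efficiency as a sample-size multiplier, as Protocol 5.2 does.

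**What to change.** Reconcile Protocol 5.2 with the SAP synopsis and its missing-data paragraph through one statement in the SAP, for example:

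> About 64-66 per arm are expected to complete QuIC Part A, against 74 evaluable per arm in Protocol 5.2. Power for a 4-point difference (SD 8, two-sided 5%) is about 80-81% for the t-test. For Mann-Whitney it is about 74-75% at the efficiency of 0.864 used in Protocol 5.2 (about 78-80% if near-normal efficiency of 0.955 is assumed), and it depends on the score distribution.

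If the protocol is revised, cross-reference this from 5.2 and say whether the 25% was meant to cover questionnaire non-completion. Leave simulated, distribution-specific power and the superseded target out of the inserted text.

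The cost is wording only. The SAP reports that enrolment closed once 198 were enrolled, and nothing here changes enrolment, the test, alpha or the analysis set. The price is openly stating that the fallback may have less than the 80% power implied by 5.2.

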3.1.2. Secondary Endpoints

The secondary endpoints will compare the following measures between the two arms: (1) subjective comprehension scores on the QuIC (part B) instrument and the modified DICCT instrument, (2) state anxiety scores on STAI instrument, (3) satisfaction scores, (4) time taken for information location, and (5) patient consent rates on parent clinical trials.

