- The Rapid Estimate of Adult Literacy Revised (REALM-R, a health literacy measure) will be scored as described in (Bass et all, 2003): words “fat”, “flu”, and “pill” will not be scored.
- The New Vital Sign (a health literacy measure) will be scored as described in (Weiss et al, 2005)
- The State-Trait Anxiety Inventory (STAI) will be scores as described in its manual (Spielberger et al, 1983)

NCT02081248

- The Consent Form Satisfaction Survey will be summarized by its total score as the sum of responses to its seven Likert questions (0-4).
- The Deaconess Informed Consent Comprehension Test will be scored as described in (Miller et al, 1996). The total score ranges between 0-28.

Primary Endpoint and Data Analysis:

The primary endpoint of BMT CTB 1205 is the mean comprehension score on the Quality of Informed Consent (part A) instrument.

The primary analysis will be performed using all patients who completed the Quality of Informed Consent (Part A) and will be based on the two sample t-test or, if the t-test assumptions are violated, with Mann-Whitney test. The statistical significance will be declared if the P-values of a two-sided test <0.05 .

The following non-primary analyses will use all randomized patients with possible exclusion of clinical trials protocols with high missing data rates. Non-primary analysis will rely on linear regression models with multiple imputations to address missing data issues.

Analysis of interactions between the randomized assignment and (1) the trial protocol, (2) literacy level (REALM-R), (3) income, (4) age groups, (5) education level. The statistical significance of interactions will be declared at ALPHA 0.01 (Bonferroni adjustment for 5 tests). If the interaction test is significant then post-hoc comparisons between the ETRIC and standard consent groups will be performed for each level of a categorical variable.

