Alternative analyses: To satisfy model assumptions we will consider the use of monotone variance-stabilizing transformations for continuous variables. If, however, the model specification continuous being inadequate (non-Gaussian distribution of model residuals, outliers, etc.), we proceed with generalized estimating equations (GEE) instead of the mean linear regression. To accommodate potential dependence of responses within clinical trial sites “leave-one-site-out” cross-validation will be used to estimate robust standard errors of the test statistic (the regression coefficient of the ETRIC effect in either mean or median regression models).

Secondary Endpoints and Final Analysis:

Secondary continuous endpoints are subjective comprehension, anxiety, satisfaction, and information location. The only secondary binary endpoint is the consent rate for the parent clinical trial.

Analysis of secondary endpoints: By analogy with the primary endpoint, the secondary endpoints (1) subjective comprehension scores on the Quality of Informed Consent (part B) instrument, (2) the modified Deaconess Informed Consent Comprehension Test instrument, (3) state anxiety scores on State Trait Anxiety Inventory instrument, (4) overall satisfaction score will be analyzed using t- or Mann-Whitney tests as appropriate. The analysis of time to information location will be performed with generalized linear models (GLM) models using the LOG link function if nonlinearity needs to be accounted for. The comparison of consent rates between ETRIC and standard consent forms will be performed with GEE using the LOGIT link. The GEE model will control for the fixed effect of trial protocol and for the dependence within the clinical trial site. The statistical significance of the ETRIC intervention on each of the secondary endpoints will be declared if the P-values of two-sided Wald test with robust standard errors <0.05. Missing data will be treated by analogy with the primary outcome using multiple imputations and tipping-point analysis.

Patients to Include:

All patients who completed the Quality of Informed Consent (part A) survey will be included in the primary data analysis. All enrolled patients will be included in the data analysis of secondary endpoints.

Content of Tables

Tables:

Table 1: Demographics and baseline characteristics by treatment arm

Table 2: Study endpoints by treatment arm

Table 3: Interaction analyses for the Quality of Informed Consent (part A)

NCT02081248

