Table 4: Adjusted analysis of Quality of Informed Consent (part A) instrument

Figures:

Figure 1: CONSORT diagram (a separate file is attached for a template)

Figure 2: Bar graphs of means and standard errors for the primary and secondary endpoints in ETRIC and Standard consent forms (below is an example).

[figure not shown]

Table 1: Demographics and baseline characteristics by treatment arm

	Treatment Arm		P-value
	ETRIC N(%) or N(M+/-SE)	Standard N(%) or N(M+/-SE)	
Gender			
- Female (N)			
- Male (N)			
Hispanic/Latino			
- Yes (N)			
- No (N)			
- Missing (N)			
Race			
- White (N)			
- Black (N)			
- Other (N)			
- Missing (N)			

NCT02081248

The Trial Protocol			
- BMT CTN 0901 (N)			
- BMT CTN 1101 (N)			
- BMT CTN 1203 (N)			
- BMT CTN 1301 (N)			
Income (\$)			
- <20,000 (N)			
- 20,000-39,999 (N)			
- 40,000-59,999 (N)			
- 60,000-79,999 (N)			
- 80,000-99,999 (N)			
- 100,000+ (N)			
- Missing (N)			
Age (years)			
Education Level			
- Education Group 1 (N)			
- Education Group 2 (N)			
- Education Group 3 (N)			
- ...			
- Missing (N)			

Table 2: Study endpoints by treatment arm

	Treatment Arm		
	ETRIC N(%) or N(M+/-SE)	Standard N(%) or N(M+/-SE)	P-value
Quality of Informed Consent (part A)*			
Quality of Informed Consent (part B)			
Modified Deaconess Informed Consent Comprehension Test			
The State Trait Anxiety Inventory Score			
Overall Satisfaction Survey			
Averaged Time to Information Location (sec)			
- Where can you find the main goal of the study?			
- Where can you find who to contact if you have questions about the study?			
- Where can you find the risks to taking part in the study			
- Where can you find how to leave the study?			
- Where can you find what you will have to do in the study?			
Consent Rate of Parent clinical Trial (Y/N)			

NCT02081248

 - BMT CTN 0901 (N) - BMT CTN 1101 (N) - BMT CTN 1203 (N) - BMT CTN 1301 (N) 			
--	--	--	--

*primary outcome

Table 3: Interaction analyses for the Quality of Informed Consent (part A)

	Treatment Arm		
	ETRIC (N) M +/-SE	Standard (N) M +/-SE	P-value
The Trial Protocol			

 - BMT CTN 0901 (N) - BMT CTN 1101 (N) - BMT CTN 1203 (N) - BMT CTN 1301 (N) 			
Literacy level (REALM-R)			

 - Missing (N) 			
Income (\$)			

 - <20,000 (N) - 20,000-39,999 (N) - 40,000-59,999 (N) - 60,000-79,999 (N) - 80,000-99,999 (N) - 100,000+ (N) - Missing (N) 			

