Age (years)			
Education Level			

 - Education Group 1 (N) - Education Group 2 (N) - Education Group 3 (N) - ... - Missing (N) 			

* P-values column will provide global interaction tests and P-values for post-hoc comparisons between the regression coefficients ETRIC and standard consent groups (Missing Data group will be excluded from calculations).

Table 4: Adjusted analysis of Quality of Informed Consent (part A) instrument

Table will report the results of a parsimonious regression model

	Regression coefficient (+/-SE)	P-value
(Model intercept)	Coef (SE)	
ETRIC	Coef (SE)	
Covariate 1		

 - Category 1 	Coef (SE)	

NCT02081248

- Category 2	Coef (SE)	
- ...		
- Reference Category	0 (-)	
Covariate 2		
- Category 1 of Covariate 2	coef (SE)	
- Category 2 of Covariate 2	coef (SE)	
- ...		
- Reference Category of Covariate 2	0 (-)	
...		

P-values column will provide global P-values and P-values of post-hoc comparisons between versus the reference category. Indicator of ETRIC will always be included in the regression model; inclusion of other variables will depend on their significance level (<0.05).

References:

1. Steven Joffe, E. Francis Cook, Paul D. Cleary, Jeffrey W. Clark, Jane C. Weeks Quality of Informed Consent: a New Measure of Understanding Among Research Subjects *Journal of the National Cancer Institute*, Vol. 93, No. 2, January 17, 2001
2. Roderick Little and Donald Rubin. Statistical Analysis of Missing Data, 2002, 2nd ed., Wiley
4. Spielberger, C. D., Gorsuch, R. L., Lushene, R., Vagg, P. R., & Jacobs, G. A. (1983). Manual for the State-Trait Anxiety Inventory. Palo Alto, CA: Consulting Psychologists Press.
7. Little R. and Rubin D, Statistical Analysis with Missing Data. 2nd ed, 2002, Wiley

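### Does the SAP's 0-28 range for the Deaconess test need correcting, when the protocol describes eight elements rated 0-2?

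*SAP*

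**What the plan says.** The SAP's section on survey instrument scoring has one bullet for this instrument. It reads "The Deaconess Informed Consent Comprehension Test will be scored as described in" the 1996 publication of the test, followed by "The total score ranges between 0-28". The matching entry in the SAP's reference list is "The Deaconess Informed Consent Comprehension Test: an assessment tool for clinical research subjects", which is the paper on the test in its original form.

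Elsewhere both documents name a modified version:

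- Protocol Section 3.1.2 lists "subjective comprehension scores on the QuIC (part B) instrument and the modified DICCT instrument" as the first group of secondary endpoints, and the SAP synopsis repeats this.
- The SAP paragraph on analysis of secondary endpoints names "the modified Deaconess Informed Consent Comprehension Test instrument".
- The row in the SAP's Table 2 shell is labelled "Modified Deaconess Informed Consent Comprehension Test".

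Protocol Table 4-4-1 and Section 4.4.2 describe the modified test as a semi-structured interview on eight disclosure elements. Section 4.4.2 names all eight. Answers are rated 2, 1 or 0, and a composite is formed, but neither place says how. Protocol Tables 4-4-3, G-1 and G-2 give 11 as the number of items.

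**The concern.** A scoring section should fix the scale on which an endpoint is measured. Here the SAP leaves out the word modified, cites only the original instrument's paper and states a ceiling that the protocol's description does not produce. Two things could be at stake.

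The first is interpretation. A reader who takes 28 as the maximum would misjudge how much patients understood if the form in use tops out lower.

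The second is more substantive. If a scoring rule written for one version of the test were applied to a different version, the wrong set of responses might be added up, and the choice of responses can affect a comparison between arms. The modified DICCT is also the only comprehension measure rated by a coordinator from open-ended answers, so it is a useful check on the self-completed Quality of Informed Consent (QuIC) scores.

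**Working it through.** **Step 1: try to reproduce 28.** The maximum total is the number of rated units times the maximum per unit, assuming an unweighted sum. That assumption is mine; the protocol does not state it.

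| Source | Units | Maximum per unit | Maximum total |
|---|---|---|---|
| Protocol Table 4-4-1 and Section 4.4.2 (elements) | 8 | 2 | 8 × 2 = 16 |
| Protocol Tables 4-4-3, G-1, G-2 (items, if each carries one 0-2 rating) | 11 | 2 | 11 × 2 = 22 |
| SAP scoring bullet for the DICCT | not given | not given | 28 |
| SAP scoring bullet for the satisfaction survey | 7 | 4 | 7 × 4 = 28 |

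At 2 points per unit, 28 needs 28 / 2 = 14 rated units. That is 14 − 8 = 6 more than the elements described and 14 − 11 = 3 more than the items listed. Spreading 28 over the described units needs 28 / 8 = 3.5 or 28 / 11 = 2.55 points each, and neither is a whole-number scale. So 28 is not reproduced from the protocol's description of this instrument.

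The satisfaction survey, in the bullet just above, does give exactly 28. The figure may have been carried over from there, or it may belong to the unmodified test. The study form may also really total 28, through more ratings than the protocol describes or through a composite that is not a plain sum. The documents do not contain the form or its scoring key and cannot settle which. The figure of 22 is conditional, not a ceiling, because nothing says that each listed item receives exactly one rating.

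**Step 2: trace where the stated maximum would enter an analysis.**

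- *Arm comparison.* The SAP uses a t-test or Mann-Whitney test and also refers to a Wald test with robust standard errors. None takes the scale maximum as an input. If the score is rescaled as Y′ = a + bY with b > 0, the t and Wald statistics become (b × difference) / (b × SE), which is unchanged. Ranks are unchanged too.
- *Missing data.* Multiple imputation and the tipping-point analysis work on the observed scores and the imputation model's parameters. The SAP does not truncate imputed values at a maximum.
- *Outputs.* Table 2 reports N with mean and standard error by arm. Figure 2 is "Bar graphs of means and standard errors for the primary and secondary endpoints". Neither expresses a score as a percentage of a maximum. Tables 3 and 4 concern QuIC Part A only.
- *Sample size.* Protocol Section 5.2 rests on a 4-point difference and a standard deviation of 8 on QuIC Part A. The DICCT plays no part.
- *Thresholds.* No cut-off or responder definition is built on the DICCT.

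**Step 3: ask what could change a result.** Only the choice of ratings to add, and how to add them, could do so. The SAP records that enrolment closed in August 2016, and it was drafted on 17 September 2016. Assessments fall within 7 business days of the consent discussion, so the form was already fixed by then. It is the same form in both arms.

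**The case for a change.** The strongest case for a change is that this is more than a mistyped number. The protocol separates the two instruments by citation: one reference for the original test, and that reference plus two others for the modification. The SAP's scoring bullet cites only the first. Read literally, the SAP gives a scoring rule for an instrument it does not analyse and none for the one it does. A patient with full understanding of eight elements would score 16, and a reader who took 28 as the ceiling would see 16 / 28 = 57%. Correcting this would cost one sentence.

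Much of that stands. The bullet is loosely worded, and the figures 8, 11 and 28 are not reconciled anywhere. The case still falls short of requiring a change, for three reasons:

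- The 57% reading matches no planned output. It describes a possible misreading by someone who ignores the form, and it applies equally to both arms.
- The literal reading is unlikely to be followed. The protocol gives the rating rule for the modified test, and the SAP's endpoint list and Table 2 name that test. An analyst holding the completed forms would combine the ratings recorded on them.
- The documents offer no correct value to put in place of 0-28. Writing 0-16 would assume an unweighted sum over eight ratings. Writing 0-22 would assume one rating per listed item. Either might be wrong.

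**Conclusion.** The inconsistency is genuine and minor. The SAP's 0-28 does not follow from the protocol's eight elements (16 if summed) or from its 11 listed items (22 if each has one 0-2 rating), and its origin cannot be determined from the documents. No change to the plan follows, because there is nothing to gain in the analysis. The stated maximum is not an input to any test, imputation, table, figure or sample-size step, so correcting it alone would change no result. What remains is a routine task when results are reported: look at the study form and state the range of the score as it was actually computed.

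This conclusion rests on two assumptions. The same form and scoring were used in both arms, which fits the single description in the protocol. The analyst scores the modified test as administered, rather than forcing the original test's rule onto it. If the second failed, the set of ratings being summed could differ and this one secondary comparison could be affected. The primary endpoint and the sample size would not be.
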